# **15 RESEARCH METHODS**

# 15.1 Study design

This study is a multi-country, multi-centre, hospital-based case-control study with test-negative controls (TNCC design).

A combination of primary and secondary data collection will be used to obtain the relevant data.

# **15.2 Study contributors (sites)**

This is a multi-country, multi-centre study, with hospital sites in Europe. The participating studies sites are described in Table 1.

The participating study sites are either individual hospitals or hospital networks. Depending on the hospital, the data collection will be a prospective primary data collection and in some study sites, data will additionally be retrospectively retrieved from the existing hospital databases and linked data.

For every participating study site, a site-specific protocol will be written, describing details on patient flow, data collection, laboratory tests and genomic sequencing.

#### Table 1. Participating study sites.

				No. of hospital
Country	Hospital name	Site (location)	Hospital population	beds/ICU beds
« complete »				

# **15.3 Study population**

The study population consists of individuals (patients), presenting at the participating hospitals during the study period, who

• meet the inclusion criteria (see Section 15.3.1) but who do NOT meet the exclusion criteria (see Section 15.3.2).

#### AND

• are hospitalised and meet the SARI case definition (see Section 15.6.2)

#### 15.3.1 Inclusion criteria

Individuals (patients) need to fulfil the following inclusion criteria:

• Ever eligible for COVID-19 vaccination following the national/regional immunisation recommendations prior to hospital admission

AND

• Willing and able to provide informed consent, when applicable, obtained from the patient or from the patient's Legally Acceptable Representative(s) (LAR)

#### 15.3.2 Exclusion criteria

- COVID-19 hospitalisation within 3 months prior to the current admission. Hospital transfers are not considered as a prior hospitalisation
- Cannot be swabbed due to severe septum deviation, obstruction, or other conditions that contra-indicate swabbing
- Received last vaccine dose with other than EMA-approved COVID-19 vaccine brand (EMA approval status at time of hospitalisation)

# 15.4 Study period

#### « Modify as appropriate »

From month 202[X], with a minimum duration of 12 months and an expected duration of two years

#### **15.5 Study outcomes**

#### « Study outcomes to be aligned with study objectives. »

The outcome of interest for the primary analysis will be SARS-CoV-2 detection in patients hospitalised with SARI symptoms. SARS-CoV-2 infection should be laboratory-confirmed by Reverse transcription polymerase chain reaction (RT-PCR) or another RNA amplification system with at least the same sensitivity as RT-PCR (e.g. Transciption mediated amplification (TMA)). As the SARS-CoV-2 testing practices might change over time, the test requirement for confirmation of COVID-19 disease might

# **C VIDRIVE**

Version 4.0

be revisited. The impact of such revisions on the potential for disease misclassification will be considered.

The secondary outcomes include:

• Detection of SARS-CoV-2 genetic variants in patients hospitalised due to laboratory-confirmed SARS-CoV-2.

The exploratory outcomes include:

- Hospitalisation due to laboratory-confirmed SARS-CoV-2 by level of severity: (i) hospital admission without intensive care unit (ICU) admission and without in-hospital death, (ii) ICU admission without in-hospital death and (iii) in-hospital death.
- Clinical and laboratory features of critical COVID-19 disease cases in patients hospitalised due to laboratory-confirmed SARS-CoV-2. Critical COVID-19 disease is defined as being admitted to an ICU.

# **15.6 Definitions**

#### 15.6.1 Hospitalised patient

Persons admitted to the hospital with overnight stay. In case of referral to another hospital, the date of hospital admission is defined as the date of first admission.

#### 15.6.2 SARI patient (possible COVID-19 cases)

A possible COVID-19 case is defined as a hospitalised person with a suspicion of a respiratory infection with **at least one** of the following symptoms:

- cough
- fever
- shortness of breath
- sudden onset of anosmia, ageusia or dysgeusia

with symptom onset within the last 14 days prior to hospital admission as per ECDC definition [10].

#### 15.6.3 Test-positive case

A study participant who:

• meets the SARI case definition (see Section 15.6.2)

AND

tests positive in at least one SARS-CoV-2 RT-PCR or similar molecular assays with specimen(s) collected between 14 days prior to and up to [72 hours] after hospital admission.

 72 hours after hospital admission is the maximum delay accepted for testing. Each brand-specific protocol will specify whether the study uses a delay of 24 hours, 48 hours or 72 hours after admission.

#### 15.6.4 Test-negative control

A study participant that:

• meets the SARI case definition (see 15.6.2)

AND

tests negative for all SARS-CoV-2 RT-PCR or similar molecular assays with specimen(s) collected between 14 days prior to and up to [72 hours] after hospital admission.. Test-negative controls must have a negative result for the RT-PCR or similar molecular assay within [72h] of hospital admission.

 72 hours after hospital admission is the maximum delay accepted for testing. The brand-specific protocol will specify whether the study uses a delay of 24 hours, 48 hours or 72 hours after admission.

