**C VIDRIVE** 

# **17 LIMITATIONS OF THE RESEARCH METHODS**

The COVID-19 pandemic is unprecedented, unpredictable and poses challenges for the postmarketing evaluation of the COVID-19 vaccines. The following challenges and limitations for the realworld evaluation of the COVID-19 vaccines have been identified at the time of writing this protocol.

The sensitivity of the SARI case definition is imperfect and potential COVID-19 cases might not be included in the study. This will, however, not bias the CVE estimates unless vaccination affects the presentation of the SARI symptoms. Until now, it is unknown whether COVID-19 vaccination induces a milder course of disease.

As for other epidemiological study designs, the results from TNCC study designs can be biased due to misclassification of disease status using diagnostic assays with imperfect sensitivity and specificity. Low sensitivity and low specificity are expected to bias the CVE estimates downwards with the bias resulting from low specificity being more substantial than the bias from low sensitivity [24]. To minimise misclassification bias, laboratory confirmation based on RT-PCR or another RNA amplification system with at least the same sensitivity and specificity is required for the current study. The specificity of RT-PCR for the diagnosis of COVID-19 is high (>99.5%) while its sensitivity depends on various factors, including timing of sampling, type of specimen and sampling technique. In hospitalised patients, the clinical sensitivity of PCR decreased with days post symptom onset with >90% clinical sensitivity during the first 5 days after symptom onset and 70%-71% from days 9 to 11 [25]. Also, the sensitivity is higher for lower respiratory samples than for upper respiratory tract samples [26], and a good sampling technique is required to obtain better results. To explore any potential bias due to disease misclassification, information on type of specimen will be collected and sensitivity analyses regarding time between symptom onset and swabbing will be performed. Guidance on collecting and handling specimens for the diagnosis of COVID-19 will be given as part of study staff training.

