The SARS-CoV-2 positivity rates within the SARI patients varies over time with the observed positivity rates since the start of the COVID-19 pandemic ranging from 20% to 80% (FISABIO, personal communication), implying that the potential case to control ratio would vary from 1:4 to 4:1 depending on calendar time. Future SARS-CoV-2 positivity rates in SARI patients are difficult to predict as they depend on both the successfulness of the COVID-19 vaccination programmes and the circulation of other respiratory pathogens. In case-control studies, the ideal number of controls is typically 1 to 3 times the number of cases [27]. To allow optimising the case-control ratio conditional on calendar time (with the latter being an important confounder in CVE studies), we allow for the possibility to 1) sample other hospital controls or modify the case capture definition in case the positivity rate would be high, and – when feasible and resource saving— to 2) restrict the number of controls per case in case the positivity rate would be low.

Confounding is a substantial concern for real-world studies on the effectiveness of COVID-19 vaccines.

As a result of the huge demand for COVID-19 vaccines and initially limited vaccine supplies, most European countries prioritised the vaccination of elderly people, residents and personnel in long-term

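### A SARI patient negative in the chosen window but positive on a later test in the same admission stays a control, and Annex 4 does not record the later result

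*Protocol*

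**What the plan says.** Section 15.6.4 of the protocol defines a control as a SARI patient who "tests negative for all SARS-CoV-2 RT-PCR or similar molecular assays with specimen(s) collected between 14 days prior to and up to" the chosen limit after admission. It adds: "Test-negative controls must have a negative result for the RT-PCR or similar molecular assay within" that limit of admission. The limit is a placeholder set at 72 hours, and the footnote says "The brand-specific protocol will specify whether the study uses a delay of 24 hours, 48 hours or 72 hours after admission". The case definition in 15.6.3 uses the same window: a case "tests positive in at least one SARS-CoV-2 RT-PCR or similar molecular assays with specimen(s) collected between 14 days prior to and up to" that limit. The abstract repeats both definitions.

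Neither definition mentions specimens taken after the window. The only COVID-19 illness that excludes a patient under 15.3.2 is an earlier one: "COVID-19 hospitalisation within 3 months prior to the current admission". In Annex 4 the laboratory block holds one swab date and one SARS-CoV-2 result per patient, and the coding note for the swab date refers only to tests in the 14 days before admission.

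Section 17 says low sensitivity biases CVE downwards. It gives clinical sensitivity above 90% in the first 5 days after onset and 70%-71% on days 9 to 11, and notes that "the sensitivity is higher for lower respiratory samples than for upper respiratory tract samples". It reports positivity among SARI patients between 20% and 80%. The abstract's limitations say the bias grows with positivity. The planned responses are a shorter onset-to-swab time, recording of specimen type, guidance in staff training, and a sensitivity analysis on onset-to-swab time.

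**The concern.** Repeat testing of a patient who still looks infected is one way a false negative comes to light. The control definition uses repeat tests only up to the end of the window. A patient negative on an upper-airway swab at admission and positive on a lower-airway sample on day 4 satisfies every element of 15.6.4 and is analysed as a control.

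The choice of window makes this sharper. A first positive at 60 hours makes the patient a case under the 72-hour option and leaves the same patient a control under 24 or 48 hours. The master protocol thus accepts that result as evidence of COVID-19 in one brand's study and disregards it in another's, although one of its stated purposes is to harmonise case definitions.

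The SAP could not repair this alone. If the minimum dataset does not carry the later result, no central analysis can find these patients or count them. The onset-to-swab analysis sorts patients by timing and makes no use of later results.

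**Working it through.** The protocol gives no figure on this point, so there is none to reproduce. The check uses an expected 2x2 table.

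**Inputs from the protocol.** True CVE 80% and coverage among controls v = 60% (both from 15.11.1.1); sensitivity Se of 0.90 and 0.70 (section 17); positivity π of 20%, 50% and 80% (range in section 17).

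**Assumptions.** Specificity 1 (section 17 says above 99.5%); sensitivity and retesting unrelated to vaccination; one exposure group; π taken as the true infected share. The share f of false negatives found after the window is not in the documents; 10% to 50% is shown.

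**Formulas.**
- Vaccination odds in true controls: 0.6/0.4 = 1.5.
- Vaccination odds in cases: (1 − 0.8) × 1.5 = 0.3, so 0.3/1.3 = 0.2308 of cases are vaccinated and 0.7692 are not.
- False negatives left per true control: g = π(1 − Se)(1 − f)/(1 − π).
- Odds in the analysed control group: (0.6 + 0.2308g)/(0.4 + 0.7692g).
- Observed CVE = 1 − 0.3/(those odds).

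**Worked case, π = 50%, Se = 0.90.**
- f = 0: g = 0.1, odds 0.6231/0.4769 = 1.306, CVE = 77.0%.
- f = 10%: g = 0.09, odds 0.6208/0.4692 = 1.323, CVE = 77.3%.
- f = 50%: g = 0.05, odds 0.6115/0.4385 = 1.395, CVE = 78.5%.

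**Results (true CVE 80%, coverage 60%).** The last column is the part that depends on later positives, taken before rounding.

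| Positivity | Se | f = 0 | f = 10% | f = 50% | Avoidable part, points |
|---|---|---|---|---|---|
| 20% | 0.90 | 79.2% | 79.3% | 79.6% | 0.1-0.4 |
| 20% | 0.70 | 77.8% | 78.0% | 78.9% | 0.2-1.1 |
| 50% | 0.90 | 77.0% | 77.3% | 78.5% | 0.3-1.5 |
| 50% | 0.70 | 71.7% | 72.5% | 75.6% | 0.8-3.9 |
| 80% | 0.90 | 69.3% | 70.3% | 74.3% | 0.9-5.0 |
| 80% | 0.70 | 54.7% | 56.5% | 65.0% | 1.8-10.3 |

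The positivity in section 17 is what tests observed. A true share of 50% would show as 0.50 × 0.90 = 45% or 0.50 × 0.70 = 35% positive.

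**The opposite error.** Suppose the later positives are hospital-acquired infections in correct controls, affecting a share h of unvaccinated controls and h(1 − CVE) of vaccinated ones. Removing them gives OR = 0.2 × (1 − h)/(1 − 0.2h). For an assumed h = 1%: 0.2 × 0.99/0.998 = 0.198, CVE 80.2%. For h = 5%: 0.2 × 0.95/0.99 = 0.192, CVE 80.8%.

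**The case against.** The strongest reply is that a window has to end somewhere. A bounded window ties the test to the episode that caused admission, and retesting inside it is already used, because every test in it must be negative. The protocol also admits the sensitivity bias, states its direction, plans responses to it, and leaves the full list of sensitivity analyses to the SAP. All of that stands, but none of it covers a result that Annex 4 does not collect.

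A reader might infer that these patients are known false negatives and that every CVE is therefore biased towards zero. The documents do not support this. A first positive several days into the stay can be a hospital-acquired infection, the protocol gives no means of telling the two apart, and the longer the gap the likelier that explanation becomes. At 60 hours it is a weak objection, since the 72-hour option itself counts such a positive as making a case.

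A reader might also take the whole shortfall, such as 80% falling to 71.7%, as the cost of this gap. That is the bias from all false negatives, most of whom may never be retested. Only the increment in the last column of the table is at issue. At 10% detection and 50% positivity it is 0.3 to 0.8 points, small beside the 30-point interval length the study is sized for, although a larger sample would not remove it.

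Finally, a reader might want all later positives within 14 days of onset dropped from the primary analysis. That rule would work poorly. For a patient admitted on day 11 the 72-hour window already ends on day 14, so the rule never operates where sensitivity is lowest. For one admitted on day 1 it runs for ten further days in hospital, when acquired infection is more plausible. Testing follows routine practice (15.9.1), so if unvaccinated patients were retested more often, they would be removed preferentially and CVE would rise artificially.

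**Conclusion.** The gap is real and modest. Under the text as it stands, a patient negative in the window and positive later in the same admission is analysed as a control, and the minimum dataset cannot show how many there are. Those who are false negatives lower CVE. The amount cannot be fixed from the documents, because neither the share of controls retested nor the share then found positive is given. At 50% positivity, 60% coverage and true CVE 80%, the avoidable part is about 0.3 to 1.5 points at sensitivity 0.90 and 0.8 to 3.9 at 0.70, if 10% to 50% of false negatives are found later. It is smaller at 20% positivity and larger at 80%. The clearest fault is the inconsistent treatment of a positive between the chosen limit and 72 hours under the 24- and 48-hour options. After 72 hours the case for exclusion is uncertain enough that it should be examined in a sensitivity analysis and left out of the primary analysis.

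**What to change.** 1. In 15.6.4 and the abstract, state that a patient with any positive molecular test up to 72 hours after admission cannot be a control, even where the brand-specific protocol uses 24 or 48 hours. If that positive falls after the chosen window, the patient is neither case nor control and is counted in the attrition diagram.
2. Add an Annex 4 field for a first positive after the window in the same admission (yes/no, with date), taken from routine records.
3. Pre-specify a sensitivity analysis that excludes controls with a positive after 72 hours, by days since admission, and report their number by vaccination status.

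The cost is a sentence in two places, one field, one attrition line and one sensitivity analysis, with no additional testing. A few controls are lost. Some hospital-acquired infections may be removed, which would move a true 80% to about 80.2%-80.8% if 1%-5% of unvaccinated controls were affected. Retesting may depend on vaccination status; the counts by vaccination status would help to judge this.

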# **15.7 SARI patient identification**

Depending on the study site, the SARI patient identification will be different. Hospitalised SARI patients will be identified prospectively (e.g. during consultation in the ED or during a pneumology consultation) or retrospectively by hospital database search or from respiratory samples sent to the virology laboratory.

«For every participating study site, the patient flow will be documented in detail.»

# **15.8 Exposure (COVID-19 vaccination)**

#### 15.8.1 Exposure definitions

#### « Exposure outcomes to be aligned with study objectives. »

- 1. Vaccinated with at least one dose: vaccinated with **at least 1 dose** of the COVID-19 vaccine brand of interest  > 14 days prior to SARI symptom onset.
- 2. Completed primary series vaccination: **completed a primary series** with the COVID-19 vaccine brand of interest  > 14 days prior to SARI symptom onset.

- At least one additional COVID-19 vaccine dose: any COVID-19 vaccine dose with the brand of interest  given as last dose > 14 days prior to SARI symptom onset to subjects who previously completed a primary series with any COVID-19 vaccine(s) .
- 4. Previously vaccinated but did not receive the last additional dose of interest: previously completed at least a primary series with any COVID-19 vaccine prior to SARI symptom onset, and was **eligible**  **to receive the last additional dose of interest but did not receive it**.
- Recently vaccinated: vaccinated with any COVID-19 vaccine <= 14 days prior to SARI symptom onset .
- 6. Unvaccinated: did **not receive any COVID-19 vaccine dose.**
- 7. Other: additional vaccine exposure case definitions might be defined depending on the reallife use of the COVID-19 vaccines.

 *The COVID-19 vaccine with brand of interest must be EMA approved.* 

 Throughout the protocol, additional dose refers to booster doses (1st, 2nd, 3rd...). COVID-19 vaccine dose will be classified as primary (P) or additional dose (N) by expert consensus.

 For its secondary objective, the Study Requestor may define specific exposures based on the number of COVID-19 vaccine doses and type(s) of the COVID-19 vaccine doses given prior to the last dose.

 at least 3 months since last dose.

 Recently vaccinated patients will not be considered protected by the last vaccine dose. Their data use will be specified in the statistical analysis plan. This applies to both primary series and additional doses.

# 15.8.2 Exposure ascertainment

Information on all prior COVID-19 vaccine doses will be collected. Vaccination status, vaccination date, dose and vaccine brand information are required. When feasible, batch number will be collected. Depending on the study site, the source for exposure ascertainment will be different and may include vaccination registry, medical records or vaccination cards. For every participating study site, the source documentation and its validity will be described in detail in the study site-specific study protocol.

Patients that cannot be classified into one of the exposure categories (i.e. vaccination status is unknown) will be excluded.

Context information on national/regional COVID-19 immunisation recommendations (priority groups by vaccine brand), SARS-CoV-2 genetic variant circulation and COVID-19 vaccine label information (including licensed age groups, contraindications, number of doses and timing between doses) will be collected.

# **15.9 Outcomes**

#### 15.9.1 Laboratory-confirmed SARS-CoV-2

Respiratory specimens will be collected from those patients eligible for the study and as per routine clinical practice. Only study sites where laboratory confirmation is done by RT-PCR or another RNA amplification system with similar sensitivity are eligible to participate to the study. Nasopharyngeal or oropharyngeal swabs are recommended.

For every participating study site, the testing policy and laboratory methods will be described in detail in the site-specific protocol. Information as summarised in Table 2 will be collected.

Genomic sequencing will be performed using commercially available molecular kits. At every study site with prospective data collection, preferably 100% of the vaccinated SARS-CoV-2 positive cases (i.e. vaccine failures) for the brands of interest and sufficiently large proportion of the unvaccinated SARS-CoV-2 positive cases will be sequenced. The size of this proportion will be chosen to obtain a sufficient number of COVID-19 cases with the variant of interest allowing the estimation of variant-and brand-specific CVE with an expected 95% CI length  $\leq$ 70% (See Section 15.11 Sample size considerations).

For retrospective data collection sequencing data is obtained from medical records, when available.

Study site name	[to be inserted]
Sampling strategy	[all patients, selection of patients fulfilling certain criteria,]
Type of respiratory	[nasopharyngeal swab, nasal swab, oropharyngeal swab,
sample	branchoalveolar lavage fluid, sputum, other (specify)]
Blood sample	[Yes or no] serum (for serology if collected)
Type of molecular	[RT-PCR, multiplex PCR, TMA, LAMP, other (specify)]
laboratory test	
Name of molecular kit	[open]
PCR Ct value	[2-digit value ] (optional)
PCR variant screening kit	[Positions screened in the S gene (501, 484, 417, 452, others)]
Full genome sequencing	[all, random sampling]
sampling strategy	
Full genome sequencing	[Illumina, Nanopore, other]
laboratory tests	
Sequencing minimum	[value - minimum of 200 required]
nucleotide coverage	

#### Table 2. Key aspects of laboratory specimen collection and analysis

Abbreviation: LAMP loop-mediated isothermal amplification

# **C VIDRIVE**

#### 15.9.2 Hospitalisation due to laboratory-confirmed SARS-CoV-2: level of severity

The following three mutually exclusive categories will characterise the severity of the hospitalisation due to laboratory-confirmed SARS-CoV-2 disease:

- 1. Hospital admission without ICU admission and without in-hospital death
- 2. ICU admission without in-hospital death
- 3. In-hospital death

COVID-19 hospitalisation that takes place within 3 months of the first COVID-19 hospitalisation will be considered as part of the same episode.

